6.2. Treatment Period

The subject will begin treatment upon confirmation of eligibility. For visits within the Placebo-controlled Phase and Apremilast Extension Phase, an administrative window of \pm 4 days is permitted. For the Observational Follow-up visit, an administrative window of \pm 2 weeks from the last dose of investigational product (IP) is permitted.

During the treatment period, every effort must be made to ensure that subjects complete the subject questionnaires prior to any other study procedure being performed. Subjects questionnaires must always be completed prior to any efficacy assessments by the investigator or qualified designee.

During the treatment period, efficacy assessments may be performed by the investigator or qualified designee at any time during a study visit (but only after the subject has completed the

GPSS and DLQI), when required. The investigator performing efficacy assessments shall make independent observations at a given study visit and shall not review previous assessments or subject-derived data in advance of conducting the assessments.

The following evaluations/assessments will be performed at the frequency specified in the Table of Events, [Table 3](#):

- Subject reported outcomes or health-related quality of life (HRQoL)
- Concomitant medications and therapies evaluation
- Vital signs
- Weight
- Pharmacodynamic blood sampling
- Hematology panel
- Chemistry panel
- Urinalysis
- Adverse event assessments (continuously)
- Efficacy assessments (see Section [6.4](#))
- Urine dipstick pregnancy test and contraception education (prior to dosing on Day 1)
- IP dispense, return, and IP tablets count
- Photographs (optional, refer to Section [6.8](#))

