5. TABLE OF EVENTS

Table 3: Table of Events

Visit Number	Screening	Placebo-controlled Treatment Phase							Active Treatment Phase			Observational Follow-up
	1	Baseline ^a	2	3	4	5	6	7	8	9	10/ET ^b	11
Week	-5 to 0	0 (Day 1)	2 (± 4 days)	4 (± 4 days)	8 (± 4 days)	12 (± 4 days)	16 (± 4 days)	20 (± 4 days)	24 (± 4 days)	32 (± 4 days)	4 Weeks After Last Dose	
Administrative/Demographics												
Informed consent ^d	X	-	-	-	-	-	-	-	-	-	-	-
Demographics	X	-	-	-	-	-	-	-	-	-	-	-
Inclusion / Exclusion criteria	X	X	-	-	-	-	-	-	-	-	-	-
Medical history	X	-	-	-	-	-	-	-	-	-	-	-
Prior psoriasis medications	X	-	-	-	-	-	-	-	-	-	-	-
Prior / concomitant medications or therapies	X	X	X	X	X	X	X	X	X	X	X	X
Clinical and Laboratory Assessments												
Adverse events	X	X	X	X	X	X	X	X	X	X	X	X
Psychiatric evaluation ^e	-	-	-	-	-	-	-	-	-	-	-	-
Pregnancy test and contraception education ^f	X	X	-	-	-	-	-	-	-	-	X	-
Hepatitis B and C ^g	X	-	-	-	-	-	-	-	-	-	-	-
Vital signs	X	X	-	X	X	-	X	-	-	X	-	-
Height	X	-	-	-	-	-	-	-	-	-	-	-
Weight	X	X	-	-	X	-	X	-	X	X	X	-
Complete physical examination	X	-	-	-	-	-	-	-	-	X	-	-

Table 3: Table of Events (Continued)

Visit Number	Screening	Placebo-controlled Treatment Phase							Active Treatment Phase			Observational Follow-up
		1	Baseline ^a	2	3	4	5	6	7	8	9	
Week	-5 to 0	0 (Day 1)	2 (± 4 days)	4 (± 4 days)	8 (± 4 days)	12 (± 4 days)	16 (± 4 days)	20 (± 4 days)	24 (± 4 days)	32 (± 4 days)	4 Weeks After Last Dose (± 2 weeks) ^c	
Clinical laboratory evaluations ^h	X	X	-	-	-	-	X	-	-	X	-	
Psoriasis Flare Assessment ⁱ	-	-	-	-	-	-	-	-	-	-	-	
Subject Rated Outcome and Health-related Quality of Life Assessment												
Optional Assessment(s) at Selected Investigative Sites												
Photographs	-	X	-	-	X	-	X	-	-	X	-	
IP												
Dispense IP	-	X	-	X	X	X	X	X	X	-	-	
Return and count IP tablets	-	-	-	X	X	X	X	X	X	X	-	

Abbreviations: [REDACTED] ET = Early Termination Visit; FCBP = females of childbearing potential; IP = investigational product; [REDACTED]

- a All baseline assessments must be completed prior to randomization and dispensing of IP.
- b Visit 10 will serve as the Early Termination Visit for any subject who prematurely discontinues from the study.
- c All subjects who complete the study or discontinue the study early will be asked to enter the Four-week Post-Treatment Observational Follow-up Phase.
- d Written informed consent will be obtained by the Principal Investigator or designee prior to performing any study assessments.

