6.3. Observational Follow-up Period

All subjects will be followed for 28 days after the last dose of IP for AE reporting, as well as any serious adverse events (SAEs) made known to the investigator at any time following the protocol-required reporting period or end of study-, as described in [Section 10.1](#).

The following evaluations will be performed at the Follow-up Visit as specified in the Table of Events, [Table 3](#).

- Concomitant medications or therapies evaluation
- Weight
- Adverse event evaluation

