All AEs will be recorded by the investigator from the time the subject signs informed consent until 28 days after the last dose of IP as well as all SAEs made known to the investigator at any time following the protocol-required reporting period or after end of study. All adverse events (serious/non-serious) will be recorded on the CRF, the paper SAE report form (for SAEs) and in the subject's source documents. All SAEs must be reported to Amgen Global Patient Safety within 24 hours of the Investigator's knowledge of the event by recording on the CRF and submitting the SAE information using the paper Serious Adverse Event Report Form by facsimile/email directly to Amgen Global Patient Safety.

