5.2.1 Treatment-emergent Adverse Event

An AE is a treatment-emergent AE (TEAE) if the AE start date is

- On or after the date of the first dose of IP and no later than 28 days after the last dose of IP for subjects who have completed study treatment or have discontinued early by the time of database cut, or
- On or after the date of the first dose of IP for subjects who are ongoing with study treatment at the time of database cut.

If the treatment-emergent status of an AE is unclear due to a missing/incomplete start date, it will always be considered treatment-emergent, unless shown otherwise by data. Date imputation rules for missing AE start dates are described in [section 8.3.2](#).

Adverse event started more than 28 days after the last dose of IP will not be considered as a treatment-emergent AE.

5.2.2 Treatment-emergent Adverse Event Leading to Drug Withdrawal, Drug Interruption, or Death, and Drug-related Treatment-emergent Adverse Event

A TEAE leading to drug withdrawal is a TEAE for which the investigator indicates that the action taken with respect to IP is withdrawn permanently. A TEAE leading to drug interruption is a TEAE for which the investigator indicates that the action taken with respect to IP is interrupted. A TEAE leading to death is a TEAE for which the outcome is

fatal. Relationship to IP is based on the investigator's causality judgment; that is, a drug-related AE is an AE indicated by the investigator to have a suspected relationship to IP.

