7.4.1.3 Observational Follow-up Phase – 4 weeks

Subjects who complete the study or discontinue the study early, will be followed up for 28 days after the last dose of IP.

TEAEs in the Follow-up Phase will include adverse events started after and within 28 days of the last dose date. Those TEAEs will also be summarized in one of the two treatment phases.

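### The follow-up visit may fall on day 14, but adverse events must be recorded and are analysed to day 28; up to half of that period can pass without a scheduled enquiry

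*Protocol*

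**What the plan says.** **Visit timing.** The Visit 11 column of protocol Table 3 reads "4 Weeks After Last Dose (± 2 weeks" (closing bracket and footnote mark left off here). It is the only column after Visit 10/ET. Protocol Section 6.2 gives the follow-up visit an administrative window of ± "2 weeks from the last dose of investigational product (IP) is permitted". Table 3 therefore counts the two weeks around the week-4 target, while Section 6.2 as worded counts them around the last dose.

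**Recording duty.** Protocol Section 6.3: "All subjects will be followed for 28 days after the last dose of IP for AE reporting". Protocol Section 10.1 has the investigator record all adverse events from consent "until 28 days after the last dose of IP as well as all SAEs made known to the investigator at any time".

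**Analysis.** SAP Section 5.2.1 calls an event treatment-emergent if it starts "On or after the date of the first dose of IP and no later than 28 days after the last dose of IP". This limit applies once a subject has finished or stopped treatment. SAP Section 7.4.1.3 says "TEAEs in the Follow-up Phase will include adverse events started after and within 28 days of the last dose date". SAP Section 7.4.2 ends the Apremilast-exposure Period 28 days after the last dose for those subjects. SAP Section 7.4.1.1 uses the same 28-day tail in the Placebo-controlled Phase, but only for subjects who stop without entering the extension.

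**The concern.** Two different periods are attached to the same stretch of follow-up. The obligation and the analysis both run to day 28, but the visit at which adverse events are asked about may take place two weeks sooner. The documents describe no telephone call or other planned contact on or after day 28 for a subject whose Visit 11 came early.

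If that happens, the second half of the period has no planned prompt. A non-serious event on days 15 to 28 enters the database only if the subject volunteers it or the site asks on its own initiative. The SAP still places the subject in the denominator of subject incidence, and no planned output shows how far each subject's enquiry reached. Safety and tolerability is a stated secondary objective, and protocol Table 2 takes adverse events through the end of Observational Follow-up, so completeness of this period matters.

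**Working it through.** The check is date arithmetic on the documents' own figures.

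**Inputs**
- Length of the follow-up phase: 4 weeks (protocol Section 3.2).
- Visit 11: 4 weeks after last dose ± 2 weeks (protocol Table 3).
- Adverse-event period: 28 days after last dose (protocol Sections 6.3 and 10.1; SAP Sections 5.2.1 and 7.4.1.3).
- Early Termination Visit: within 4 days of the last intake (protocol Section 11.1).
- Planned size 286 and dropout 20% (protocol Section 9.3).

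**Step 1: the plan's own figure.** Section 3.2 gives about 41 weeks on study: 5 + 16 + 16 + 4 = 41. The follow-up phase is 4 × 7 = 28 days, which agrees with the adverse-event period.

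**Step 2: the window in Table 3.** Earliest visit 28 − 14 = day 14; latest visit 28 + 14 = day 42.

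**Step 3: days left without a scheduled enquiry.** For a visit on day d after the last dose, the uncovered part is max(0, 28 − d), out of 28.

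| Visit 11 on day | Days uncovered | Share of 28 days |
|---|---|---|
| 14 | 14 | 50% |
| 21 | 7 | 25% |
| 24 | 4 | 14% |
| 28 to 42 | 0 | 0% |

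The Early Termination Visit comes at most 4 days after the last intake, so it does not reach days 15 to 28.

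**Step 4: Section 6.2 against Table 3.** If ± 2 weeks were counted from the last dose itself, the post-dose part of the window would be day 0 to day 14. The week-4 target in Table 3 would then be out of window. The two statements cannot both be followed as written.

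**Step 5: which rates are touched.** Subject incidence (SAP Section 9.6.1) divides subjects with the event by all subjects analysed, so an unreported late event lowers the numerator. The exposure-adjusted incidence rate (EAIR) uses treatment duration as exposure time for subjects without the event, and treatment duration up to the first event for subjects with it. A first event after the last dose does not shorten treatment duration. Its denominator is therefore the same whether or not the event is captured, and only the numerator can be short.

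**Step 6: reach in the randomised comparison.** Under SAP Section 7.4.1.1, a subject who continues into the extension has the placebo-controlled event period closed the day before the first extension dose, so the 28-day tail does not apply. It applies to subjects who stop during Weeks 0 to 16. Assuming the 20% planning dropout all falls in that phase, 0.20 × 286 = 57.2, or about 57 subjects. This is an upper figure under that assumption.

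**The case against.** The strongest reply is that a visit window does not define the duty to collect adverse events. Sections 6.3 and 10.1 set that duty at 28 days and add serious events learned of at any later time. This stands. A reader might infer from Table 3 that a site may stop collecting at day 14 and still comply. It may not: it would meet the visit window and breach the recording rule. What is missing is a scheduled prompt; the obligation is there.

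A second reply concerns Section 6.2. Taken literally, its wording could suggest that almost the whole period may go uncovered. That reading would also allow a follow-up visit before the last dose, and it contradicts the four-week placement in Section 3.2 and Table 3. It is better read as a loose statement of the Table 3 window, and no size should be built on it.

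A third reply is about reach:
- Subjects are asked to enter the follow-up phase (Table 3, footnote c), so not every treated subject need appear in it.
- Separate Follow-up Phase summaries of adverse events are optional (SAP Section 9.6.1).
- The same window applies to both arms, and safety has no inferential testing (protocol Section 9.7).

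All of this stands and limits the point. It does not remove the gap, because the 28-day tail is also built into the treatment-emergent definition, the Apremilast-exposure Period and the placebo-controlled analysis of early discontinuers.

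**Conclusion.** The point holds as a gap in planned safety ascertainment. An in-window Visit 11 can leave up to 14 of the 28 days (50%) without a scheduled enquiry, 25% for a visit on day 21, and nothing from day 28 on. Fifty percent is the worst case for one subject under Table 3. The documents cannot show how many subjects are seen early.

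The possible consequence is under-counting of late, mainly non-serious, events in the numerators of subject incidence and EAIR. In the randomised comparison it is confined to subjects who stop during Weeks 0 to 16: up to about 57 of 286, if all of the planned dropout occurs there. The primary endpoint, the sample size and the efficacy analyses are not affected.

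Three further inferences are tempting and not supported:
- **Inflated exposure.** Follow-up days do not enter the EAIR denominator, so unasked days do not inflate it.
- **Bias between arms.** Nothing in the documents shows that one arm would be seen earlier than the other.
- **Loss of a pregnancy or lactation check.** Section 6.3 and Table 3 give Visit 11 only concomitant medication, weight and adverse events. The scheduled end-of-treatment pregnancy test is at Visit 10/ET, and pregnancy and lactation are reported when the site learns of them (protocol Section 10.4).

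**What to change.** 1. State one window for Visit 11, in the same words, in protocol Section 6.2 and Table 3. It should not open before the 28-day adverse-event period ends and should keep the two-week late allowance, for example day 28 to day 42 after the last dose. By the formula above, the uncovered part is then 0 of 28 days.
2. For any subject seen earlier, make one adverse-event enquiry by telephone on or after day 28.
3. In the SAP, add a count by arm of subjects whose last adverse-event contact was before day 28. This can still be done if the follow-up visits have already taken place, and it would show whether the gap mattered.

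The cost is less scheduling freedom before day 28, an occasional telephone call and one extra tabulation. No clinic visit is added.

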6.2.1. End of Treatment

An end of treatment (EOT) evaluation will be performed for subjects who are withdrawn from treatment for any reason as soon as possible after the decision to permanently discontinue treatment has been made. The end of treatment (Visit 10) assessments will also be performed for subjects who complete the study.

The investigator performing efficacy assessments shall make independent observations at a given study visit and shall not review previous assessments or subject-derived data in advance of conducting the assessments.

The following evaluations will be performed as specified in the Table of Events, [Table 3](#):

- Subject reported outcomes or health-related quality of life (HRQoL)
- Concomitant medications and therapies evaluation
- Complete physical examination
- Vital signs
- Weight
- Hematology panel
- Chemistry panel

- Urinalysis
- Adverse event evaluation
- Efficacy assessments (see [Section 6.4](#))
- Serum pregnancy test
- IP return and IP tablets count
- Photographs (optional, refer to [Section 6.8](#))

6.3. Observational Follow-up Period

All subjects will be followed for 28 days after the last dose of IP for AE reporting, as well as any serious adverse events (SAEs) made known to the investigator at any time following the protocol-required reporting period or end of study-, as described in [Section 10.1](#).

The following evaluations will be performed at the Follow-up Visit as specified in the Table of Events, [Table 3](#).

- Concomitant medications or therapies evaluation
- Weight
- Adverse event evaluation

6.4. Efficacy Assessments

• Modified static Physician Global Assessment of Genitalia (sPGA-G)

The modified sPGA-G is the assessment by the investigator of the subject's psoriasis lesions' overall severity in the genital area (labia majora, labia minora, and perineum in females; penis, scrotum, and perineum in males) at the time of evaluation. The modified sPGA-G is a 5-point scale ranging from 0 (clear) to 4 (severe), incorporating an assessment of the severity of the 3 primary signs of the disease: erythema, plaque elevation, and scaling. It is not necessary that all 3 criteria be fulfilled. The sPGA of Genitalia score is based on a combination of erythema and the secondary features (plaque elevation and/or scale). Since erythema is the most robust finding, it should be the dominant feature influencing the sPGA of Genitalia rating in the majority of cases ([Merola, 2017](#)). See [Appendix A](#) for grading criteria.

• static Physician Global Assessment (sPGA)

The sPGA is the assessment by the investigator of the overall disease severity at the time of evaluation. The sPGA is a 5-point scale ranging from 0 (clear) to 4 (severe), incorporating an assessment of the severity of the three primary signs of the disease: erythema, scaling and plaque elevation. When making the assessment of overall severity, the investigator should factor in areas that have already been cleared (ie, have scores of 0) and not just evaluate remaining lesions for severity, ie, the severity of each sign is averaged across all areas of involvement, including cleared lesions.

In the event of different severities across disease signs, the sign that is the predominant feature of the disease should be used to help determine the sPGA score. See [\(Appendix B\)](#) for grading criteria.

- **Body Surface Area (BSA)**

Body surface area is a measurement of involved skin over the whole body. The overall BSA affected by psoriasis is estimated based on the palm area of the subject's hand. The surface area of the whole body is made up of approximately 100 palms or "handprints" (each entire palmar surface or "handprint" equates to approximately 1% of total body surface area).

6.5. Safety Assessments

- **Contraception Education**

The risks to a fetus or to a nursing child from apremilast are not known at this time. Results of animal and in vitro studies can be found in the current IB.

All females of childbearing potential (FCBP) must use one of the approved contraceptive options as described in [Section 4.2](#) while on IP and for at least 28 days after administration of the last dose of the IP. The female subject's chosen form of contraception must be effective by the time the female subject is randomized into the study (for example, hormonal contraception should be initiated at least 28 days before randomization).

At screening and at baseline, and at any time during the study when a female subject of childbearing potential's contraceptive measures or ability to become pregnant changes, the investigator will educate the subject regarding contraception options and correct and consistent use of effective contraceptive methods in order to successfully prevent pregnancy.

- **Serum and Urine Pregnancy Tests for Females of Childbearing Potential (FCBP)**

A serum pregnancy test with a sensitivity of ≤ 25 mIU/mL will be required for FCBP subjects at screening and at the Early Termination Visit or Visit 10. In addition, a local urine pregnancy test kit will be provided by the central laboratory and will be performed at the site on all FCBP subjects at the Baseline Visit, prior to dosing. An unscheduled serum pregnancy test should be performed if the FCBP subject has missed a menstrual period or has a positive urine dipstick test.

- **Hepatitis B and C**

Hepatitis testing will include hepatitis B surface antigen and anti-hepatitis C antibody.

- **Vital Signs, Height, and Weight**

Vital signs, including temperature, pulse, and seated blood pressure, will be taken during the visits indicated in [Table 3](#). Height will be measured and recorded at Screening; weight will also be measured and recorded at screening and then as indicated in [Table 3](#). Body mass index (BMI) will be calculated at Screening.

- **Complete Physical Examination**

A complete physical examination includes evaluations of skin, nasal cavities, eyes, ears, lymph nodes, and respiratory, cardiovascular, gastrointestinal, neurological, and musculoskeletal systems. The complete physical examination is done at screening and at the Early Termination or Last Treatment Visit (Visit 10).

- **Psychiatric Evaluation**

Apremilast prescriber information (eg, Summary of Product Characteristics, Package Insert) includes a warning regarding depression and suicidal thoughts. Patients with chronic diseases may be prone to depression. The risks and benefits of starting or continuing treatment with apremilast should be carefully assessed if patients report previous or existing psychiatric symptoms or if concomitant treatment with other medicinal products likely to cause psychiatric events is intended. At any time during the study (post-randomization), subjects who have suicidal thoughts or behavior should be evaluated. If the psychiatrist deems the subject not to be a risk for suicide, the subject may remain in the study, but if a risk of suicide is confirmed, the subject must be discontinued from the study. If the subject is discontinued, the subject should return for the Observational Follow-up Visit.

A copy of the psychiatric evaluation report must be in the subject's source documentation, especially if the subject is confirmed not to be at risk for suicide and is continuing in the study.

- **Clinical Laboratory Evaluations**

Clinical laboratory evaluations will be performed by a central laboratory and as indicated in [Table 3](#). Clinical laboratory evaluations include complete blood count (red blood cell [RBC] count, hemoglobin, hematocrit, white blood cell [WBC] count and differential, absolute WBC counts, platelet count); serum chemistries (total protein, albumin, calcium, phosphorous, glucose, total cholesterol [TC], triglycerides, high-density lipoprotein [HDL], high-density lipoprotein cholesterol [HDL-C], low-density lipoprotein cholesterol [LDL-C], uric acid, total bilirubin, alkaline phosphatase, aspartate aminotransferase [AST; serum glutamic-oxaloacetic transaminase, SGOT], alanine aminotransferase [ALT; serum glutamic pyruvic transaminase, SGPT], sodium, potassium, chloride, bicarbonate [carbon dioxide, CO₂], blood urea nitrogen, creatinine, lactate dehydrogenase [LDH], and magnesium); as well as dipstick urinalysis (specific gravity, pH, glucose, ketones, protein, blood, bilirubin, leukocyte esterase, nitrite, and urobilinogen). Dipstick urinalysis will be performed by the central laboratory; microscopic urinalysis (epithelial cells, RBC, WBC, and casts) will be performed only if the dipstick urinalysis is abnormal.

[figure not shown]
Fasting is not required. However, if significant elevation of serum lipid(s) is observed, a fasting retest should be requested to determine whether or not elevation was caused by eating.

[figure not shown]
- **Psoriasis Flare Assessments**

Psoriasis flare represents an atypical or unusual worsening of disease during treatment ([Carey, 2006](#)). It is defined as a sudden intensification of psoriasis requiring medical intervention or a diagnosis of new generalized erythrodermic, inflammatory, or pustular psoriasis. A more typical, gradual worsening of plaque psoriasis would not be recorded as an AE.

- **Adverse Events**

Details of AE reporting may be found in [Section 10.1](#).

